Appendix II – Dose calculations and banding

Overweight patients:

1. Ideal body weight (IBW) is calculated (Lorenz formula) as:
 - i. Men: $IBW \text{ in kg} = [\text{height in cm minus } 100] - [(\text{height} - 150) \div 4]$
 - ii. Women $IBW \text{ in kg} = [\text{height in cm minus } 100] - [(\text{height} - 150) \div 2]$
2. If a patient weighs more than 1.15x their IBW, use 1.15x IBW to calculate surface area (SA).
3. Examples:
 - i. A man is 174 cm tall. His IBW is $174 - 100 - (24 \div 4) = 68 \text{ kg}$. So if his actual weight is less than 78.2 kg (68×1.15), we use his actual weight to calculate SA, but if he weighs more than 78.2 kg, we use 78.2kg to calculate SA (which gives us 1.93 m^2).
 - ii. A woman is 174 cm tall, so her IBW is $74 - 12 = 62 \text{ kg}$. So if she is over 71.3 kg, we use 71.3 kg to calculate SA (this gives us 1.85 m^2)

Fluorouracil dose banding

- First calculate the patient's surface area accurately to 2 decimal places, then calculate the exact target doses for the 5 minute 5FU bolus and 46-hour infusion
 - *For example, a patient of 1.59m^2 receiving the OxMdG regimen without dose-adjustments would have target doses of $400 \times 1.59 = 636 \text{ mg}$ Fluorouracil bolus and $2400 \times 1.59 = 3816 \text{ mg}$ Fluorouracil infusion.*
- Bolus Fluorouracil may then be rounded to the nearest 25 mg, and infusion Fluorouracil may be rounded to the nearest 50 mg.
 - *So the patient in the above example would receive 625 mg bolus + 3800 mg infusion.*
- Fluorouracil may be dose banded up to within 10% where this reflects local practice.

Oxaliplatin dose banding

- As for Fluorouracil, first calculate the patient's surface area accurately to 2 decimal places, then calculate the exact target dose.
 - *For example, the patient of 1.59m^2 receiving the OxMdG regimen without dose-adjustment would have a target dose of $85 \times 1.59 = 135.15 \text{ mg}$*
- The round the Oxaliplatin dose to the nearest 10 mg.
 - *So the patient in the above example would receive 140 mg Oxaliplatin.*

Irinotecan dose banding

- As above, first calculate the patient's surface area accurately to 2 decimal places, then calculate the exact target dose.
 - *For example, the patient of 1.59m² receiving the IrMdG regimen without dose-adjustment would have a target dose of $180 \times 1.59 = 286.2$ mg*
- Irinotecan may be dose banded up to within 5% where this reflects local practice.

Cetuximab dose banding

- As above, first calculate the patient's surface area accurately to 2 decimal places, then calculate the exact target dose.
 - *For example, the patient of 1.59m² receiving Cetuximab with the OxMdG regimen without dose-adjustment would have a target dose of $500 \times 1.59 = 795$ mg*
- Then round the Cetuximab dose to the nearest 5 mg.
 - *So the patient in the above example would receive 795 mg Cetuximab.*
- Note that overweight patients are dosed using 1.15 x ideal body weight (see Appendix II) for all chemotherapy drugs. Cetuximab doses should not however be capped to 1.15 x ideal body weight, **please** dose according to the patients actual body weight.

Appendix III – Delivery of infused treatment

The OxMdG and IrMdG regimens may be delivered in hospital but are intended as a daycase/outpatient treatment. Investigators need to consider the following issues:

Venous access:

1. Semi-permanent venous access is required, e.g.:
 - i. a single-lumen Hickman line.
 - ii. a peripheral long line (PICC, etc).
 - iii. a subcutaneous implantable port (Portacath, Infu-KT, etc).
2. Choices:
 - i. **use only single-lumen lines, not double** (double-lumen lines have a higher complication rate and **are not required** for OxMdG or IrMdG).
 - ii. for Hickman lines, use right subclavian approach not left.
 - iii. if PICC lines are used, the non-return valve type is recommended.
3. Management:
 - i. local protocol for insertion and management of the venous line is required.
 - ii. nominated staff for insertion and management of lines.
 - iii. written information for GPs and community nurses.
4. Flushing:
 - i. subcutaneous ports (e.g. PortaCath) do not need flushing between treatments.
 - ii. Hickman and PICC lines require weekly flushing.
 - iii. district nurse, carer, or district nurse should perform the weekly between-treatment flush.

Infusion pumps:

5. Suitable pumps for this study are:
 - i. elastomeric balloon infusors (e.g. Baxter 'LV5')
 - ii. battery-powered electrical pumps (e.g. Walkmed).
6. It is important that staff including out-of-hours on-call staff are familiar with the types of pump being used in the unit.
7. Note that with elastomeric pumps, flow-rates through PICC lines may be less consistent than through Hickman lines. Pumps should be allowed to complete before disconnecting, even if this takes a little longer than the intended 46 hours.

Liaison with community services:

8. Good communication with general practitioners and community nursing teams is particularly important. District nurses should be invited to attend the chemotherapy unit to learn the procedure for disconnecting chemotherapy pumps at the end of the 46-hour infusion. Written nursing protocols for care of the venous lines and pumps should be prepared for this purpose.

In-patient delivery via a peripheral vein:

9. Occasionally it is necessary to give OxMdG or IrMdG as an inpatient via a peripheral vein, e.g.:
 - i. for the first cycle if there is a waiting-list for permanent venous access insertion
 - ii. if venous access has had to be removed because of a complication
10. In this instance, the 46-hour infusion of 5FU should be divided into two 23-hour infusions, each given in 1 litre normal saline.
11. Repeated treatment administration in this way may lead to discolouration and pain over the arm veins and is not recommended. A heated pad is recommended during the Oxaliplatin infusion if OxMdG is being given.
12. Never use a peripheral vein cannula for ambulatory home chemotherapy, or to administer concentrated 5FU intended for central venous line use.

Appendix IV – Renal & hepatic function

		Cetuximab dose	Oxaliplatin dose	5FU dose
Renal function	GFR > 50 ml/min	Full	Full	Full
	GFR 30–50 ml/min	Full	Full	Full
	GFR < 30 ml/min	Full	Do not give	Reduce by 25%
Hepatic function	Bili ≤ 3x ULN and AST/ALT ≤ 2.5x ULN	Full	Full	Full
	AST/ALT > 2.5 x ULN	Full	Withhold until recovery	Withhold until recovery
	Bili > 3x ULN	Full	Reduce by 50%	Reduce by 50%

		Irinotecan dose
Renal function	GFR > 50 ml/min	Full
	GFR 30–50 ml/min	Full
	GFR < 30 ml/min	50%
Hepatic function	Bili ≤ 1.5x ULN and ALP ≤ 2.5x ULN	Full
	Bili 1.5-3x ULN or ALP > 5x ULN	50%
	Bili > 3x ULN	Omit

Notes:

- Organ function at the time of enrolment must meet the eligibility criteria (see section 8), i.e. GFR ≥ 50 ml/min, bilirubin ≤ 1.25 x ULN, alkaline phosphatase ≤ 5 x ULN and transaminase ≤ 2.5 x ULN (use either AST or ALT – it is not necessary to measure both).

2. If renal or hepatic function changes at any point after randomisation, use the table above. **Deteriorating organ function may be a sign of disease progression, so always discuss with the treating investigator.**

3. GFR: see notes in Appendix VIII for the use of Cockcroft formula to estimate GFR. For patients with a Cockcroft estimate <50 ml/min, a measured EDTA clearance (or 24 hour urinary creatinine clearance) should be obtained on at least one occasion, and this value takes precedence over the Cockcroft estimate.

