- Biochemistry (including creatinine, bilirubin, magnesium and either AST or ALT) is done at the same time as FBC.
- If patient has symptoms of possible hypomagnesemia, check magnesium level and correct as advised (see Appendix XIII).

Toxicity and dose adjustments for IrMdG**Acute cholinergic syndrome**

- Irinotecan may provoke an acute cholinergic syndrome with diarrhoea, sweating, salivation, bradycardia, etc. This may start during the drug infusion or shortly after.
- If this occurs, give atropine sulphate 0.25 mg s/c immediately. Atropine should then be given prophylactically with subsequent cycles.

Haematological

- Myelotoxicity is commoner with IrMdG than with MdG.
- Check FBC on (or up to 3 working days before) day 1 of each cycle. Delay 1 week if WBC $< 3.0 \times 10^9/l$, granulocytes $< 1.5 \times 10^9/l$ or platelets $< 100 \times 10^9/l$. Only treat when WBC and platelets are above these limits.
- If >1 delay, or 1 delay of ≥ 2 weeks occurs, reduce the Irinotecan and 5FU (bolus and infusion) doses by 20% and continue at the lower dose for subsequent cycles unless further toxicity occurs.
- If a further delay(s) for myelotoxicity occurs despite a 20% dose reduction, a further dose reduction may be made, at the discretion of the treating clinician.

Neurotoxicity

- Neurotoxicity (cerebellar) is uncommon; consider changing to alternative treatment.
- Changes in treatment should be discussed with one of the clinical coordinators.

Renal function (see also Appendix IV)

- Check serum creatinine at each cycle. If this rises $>25\%$, re-check EDTA clearance or 24-hour urinary clearance, and adjust Irinotecan and 5FU doses according to the table in Appendix IV.
- Patients with moderate renal impairment may receive irinotecan, but if GFR $<30ml/min$, the Irinotecan dose should be reduced by 50% and the 5FU dose should be reduced by 25% (see Appendix IV).

Hepatobiliary function (see also Appendix IV)

- Irinotecan and its metabolites are cleared by biliary excretion and patients with cholestasis have delayed clearance.
- LFTs should be checked before each treatment cycle. Patients with serum ALP $>5 \times ULN$ or serum bilirubin in the range $1.5-3 \times ULN$ require a 50% dose reduction of irinotecan;

patients with serum bilirubin >3 x ULN should not receive Irinotecan (please refer to Appendix IV).

- 5FU should be reduced by 50% in patients with serum bilirubin >3 x ULN (see Appendix IV).

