- Transaminase (either AST or ALT) ≤ 2.5 x ULN is required for study entry. An isolated rise in transaminase above 2.5 x ULN during treatment is likely to be treatment-related, and all treatment should be interrupted until recovery (see Appendix IV).
- Bilirubin ≤ 1.25 x ULN is required for study entry. If bilirubin rises above this limit during treatment, discuss with treating investigator as this may indicate disease progression. If treatment is to continue, please refer to table in Appendix IV.

Stomatitis

- Routine mouthcare (e.g. Corsadyl, Nystatin) is recommended, local policy on the use of these or similar drugs are acceptable.
- If mouth ulcers occur despite this, reduce the 5FU doses (bolus and infusion) by 20% and continue at the lower dose for subsequent cycles unless further toxicity occurs.
- If further toxicity occurs reduce 5FU doses (bolus and infusion) by a further 20%.

Diarrhoea

- Irinotecan may produce delayed diarrhoea which, if untreated, may become severe. Early intervention with high-dose Loperamide is highly effective. Patients must be carefully instructed and given the written information sheet, telephone contact numbers and supplies of Loperamide and CCiprofloxacin. Care should be taken that out-of-hours staff answering patient queries are familiar with the protocol.
- Patients should start Loperamide at the first loose stool: 4 mg, then 2 mg every 2 hours until 12 hours after the last loose stool (up to a maximum of 48 hours).
- If diarrhoea lasts > 24 hours, Ciprofloxacin 500 mg bd should be added. If it lasts > 48 hours, or if the patient reports symptoms of dehydration, admit acutely for rehydration and further management (eg Octreotide).
- After an episode of severe diarrhoea (grade 3-4), delay chemotherapy until full recovery then resume at 20% reduced doses of Irinotecan and 5FU (bolus and infusion).
- If diarrhoea from the previous cycle, even if not severe, has not resolved by the time the next cycle is due, delay 1 week.

Hand-foot syndrome (HFS)

- Treat symptomatically. Pyridoxine 50 mg tds by mouth or topical corticosteroids may help.
- If HFS is still a problem, reduce the 5FU doses (bolus and infusion) by 20% for subsequent cycles (no need to reduce irinotecan).
- If further toxicity occurs reduce 5FU doses (bolus and infusion) by a further 20%.

DPD deficiency; cardiotoxicity

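### The Appendix IV irinotecan table omits the AST/ALT stop set in Appendix I and gives no dose for ALP above 2.5 and up to 5 x ULN

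*Protocol*

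**What the plan says.** Protocol Appendix IV has two dose tables. The first covers cetuximab, oxaliplatin and 5FU. Its row "AST/ALT > 2.5 x ULN" withholds oxaliplatin and 5FU until recovery. The second covers irinotecan alone, and its hepatic rows use only bilirubin and ALP:

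- full dose for "Bili ≤ 1.5x ULN and ALP ≤ 2.5x ULN";
- 50% for "Bili 1.5-3x ULN or ALP > 5x ULN";
- omit for bilirubin above 3 x ULN.

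Note 1 of the same appendix repeats the entry limits, including "alkaline phosphatase ≤ 5 x ULN and transaminase ≤ 2.5 x ULN". Note 2 makes the tables operative during treatment: "If renal or hepatic function changes at any point after randomisation, use the table above".

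Appendix I (Hepatobiliary function, IrMdG) says that for an isolated AST or ALT rise above 2.5 x ULN "all treatment should be interrupted until recovery (see Appendix IV"). The IrMdG plus cetuximab section sets the same threshold and also points to Appendix IV, although it says treatment and not all treatment. For cholestasis, both sections say that patients with ALP above 5 x ULN or bilirubin of 1.5 to 3 x ULN "require a 50% dose reduction of irinotecan". Neither sets a lower ALP trigger.

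**The concern.** Appendix I sends the reader to Appendix IV for hepatic dosing, and note 2 tells sites to use the table there. For irinotecan, that table departs from Appendix I in two places.

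1. The transaminase interruption is missing. Read alone, the irinotecan table puts a patient with raised AST/ALT but low bilirubin and ALP in the full-dose row, while Appendix I stops treatment.
2. The full-dose row ends at ALP 2.5 x ULN and the half-dose row starts above 5 x ULN. When bilirubin is at or below 1.5 x ULN, nothing covers the interval between them.

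At stake is correct irinotecan dosing in patients with abnormal liver tests. Appendix I itself notes that irinotecan is cleared through the bile and that clearance is delayed in cholestasis.

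**Working it through.** The plan gives no figure to reproduce, so the check sets the two sets of rules side by side. All laboratory values are multiples of ULN.

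**Inputs**

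- Irinotecan table and notes 1 and 2: Appendix IV.
- IrMdG hepatobiliary rules, with and without cetuximab: Appendix I.
- Entry limits of bilirubin ≤ 1.25, ALP ≤ 5 and AST/ALT ≤ 2.5: section 8 and Appendix IV note 1.
- Irinotecan 180 mg/m² and the 1.59 m² example patient: Appendices I and II.

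**ALP, with bilirubin ≤ 1.5 and AST/ALT ≤ 2.5**

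| ALP | Appendix IV irinotecan table | Appendix I |
|---|---|---|
| 1.0 or 2.5 | Full | No reduction |
| 2.6, 3, 4 or 5 | No row applies | No reduction (implied, not written) |
| 5.1 or 6 | 50% | 50% |

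The gap exists only while bilirubin is at or below 1.5. Above that, the bilirubin rows give 50% or omit. Because entry requires bilirubin ≤ 1.25, this is the ordinary case, and a patient can enrol with an ALP already inside the gap.

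Uncovered share of the ALP range allowed at entry: (5 − 2.5) / 5 = 50%. This is a share of the scale and not of patients.

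Dose for the 1.59 m² example patient:

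- full dose, as Appendix I implies: 180 × 1.59 = 286.2 mg;
- half dose, if a site treats anything outside the full-dose row as 50%: 90 × 1.59 = 143.1 mg.

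**Transaminases**

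Assumed patient: AST 4, bilirubin 1.0, ALP 1.0.

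| Source | Irinotecan | 5FU |
|---|---|---|
| Appendix I, IrMdG | Interrupt | Interrupt |
| Appendix IV, first table | No irinotecan column | Withhold |
| Appendix IV, irinotecan table | Full-dose row is met | Not covered |

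The irinotecan table does not write a full dose against any transaminase value. It has no transaminase condition, so this patient satisfies its full-dose row. The conflict runs from 0 mg/m² under Appendix I to at most 180 mg/m² if the table is read alone.

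**The case against.** The strongest reply is that a site following the whole protocol would rarely go wrong.

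- **Transaminases.** Appendix I is explicit. The irinotecan table has no 5FU column, so anyone dosing IrMdG from Appendix IV must also use the first table, which withholds 5FU at the same threshold. Reaching 180 mg/m² means ignoring Appendix I and the neighbouring table, and giving irinotecan without 5FU.
- **ALP.** Full dose in the gap is the only reading that fits Appendix I. The 50% row has its own explicit condition, which a patient with ALP 3 x ULN and normal bilirubin does not meet. No sentence leads a site to 143.1 mg.
- **General safeguards.** Section 9.a requires Appendices I to IV to be consulted before any dose change and sends doubtful cases to the trials unit. Note 2 of Appendix IV adds "so always discuss with the treating investigator".
- **Cause.** The 2.5 may be a slip for 5. It may instead be that ALP was typed for ALT, since the full-dose row of the first table uses AST/ALT ≤ 2.5 x ULN. In that case the two discrepancies largely come from one mislabelled cell.

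Most of this stands as a limit on harm, and it is why the point is minor. The 90 and 180 mg/m² figures are conditional extremes and not expected doses. A slip for 5 fits the 50% row, the entry limit and Appendix I, but the document does not settle the cause. None of this makes the table agree with Appendix I or supplies the missing dose. Consulting both appendices, as section 9.a asks, is what exposes the conflict.

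**Conclusion.** The concern holds. The irinotecan table omits a stopping rule that Appendix I sets and refers to it for. With bilirubin ≤ 1.5 x ULN, it also leaves ALP above 2.5 and up to 5 x ULN without a dose. Both follow directly from the current text, and the table rows read as intact.

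This is a minor dosing-safety inconsistency confined to IrMdG patients in either arm. Their number is not given, so the count affected cannot be estimated. The halved dose assumes a site defaults to 50% outside the full-dose row, and the 180 mg/m² extreme assumes the irinotecan table is read alone. Nothing here touches the PFS analysis, the sample size or the randomisation.

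**What to change.** In the Appendix IV irinotecan table:

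1. Add a row: *AST/ALT > 2.5x ULN: Withhold until recovery*. This matches the IrMdG rule in Appendix I and the oxaliplatin and 5FU entries in the first table.
2. Reword the full-dose row as *Bili ≤ 1.5x ULN and ALP ≤ 5x ULN and AST/ALT ≤ 2.5x ULN*. This closes the gap and agrees with Appendix I and the entry limits, whichever slip produced the 2.5.

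A patient can meet more than one row (for example, AST/ALT 4 with bilirubin 2 x ULN), so it would help to state that the stricter row applies.

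The cost is a wording amendment: one added row and one corrected row, with no new data or procedures.

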Appendix V – RECIST response definitions

- RECIST (Response Evaluation Criteria In Solid Tumours) has now superseded the old WHO response criteria for solid tumours.
- The key differences are:
 - instead of measuring lesions in 2 dimensions it is now only necessary to measure the longest diameter.
 - disease is classified as measurable or not measurable but the term evaluable is no longer used.

Measurable disease:

- Disease is measurable if there is at least one measurable target lesion. Target lesions should be selected on the basis of size and suitability for repeat measurement, up to a maximum of 5 measurable lesions per organ, and up to a maximum of 10 lesions in total. These should be representative of all involved organs.
- Target lesion must be accurately measurable in at least 1 dimension, with the longest diameter ≥ 20 mm (or ≥ 10 mm with spiral CT scan). If the lesion is smaller than this then it is classed as non-measurable.
- Measurements must be taken as close as possible to the beginning of treatment and never more than 6 weeks before the start of treatment. Target lesions should be assessed by CT, MRI or CXR, not by clinical assessment alone. The same imaging modality should be used throughout for any given patient.
- When intra-venous contrast agents are given with CT, it is important to measure hepatic lesions in the same vascular phase on subsequent examinations.
- If MRI is used then the same sequence (e.g. T1 or T2 weighted images) in the same anatomical plane should be used.
- Add the longest diameters of the target lesions and report this as the **baseline sum longest diameter**. This will be used as a reference by which the tumour response will be measured.

Response definitions:

- **Complete response (CR)**: disappearance of all lesions (i.e. all evidence of disease, not just the target lesions) determined by 2 observations not less than 2 weeks apart (in *New EPOC* the 12-week assessment should be used as the confirmatory assessment; there is no need for additional confirmatory scans).
- **Partial response (PR)**: $\geq 30\%$ decrease in the sum of longest diameters of target lesions compared to baseline, with response or stable disease observed in non-target lesions, and no new lesions.

- **Stable disease (SD):** neither sufficient shrinkage to qualify for response or sufficient increase to qualify for progressive disease in target lesions, with response or stable disease observed in non-target lesions, and no new lesions
- **Progressive disease (PD):** $\geq 20\%$ increase in the sum of longest diameters of target lesions compared to smallest sum longest diameter recorded, or unequivocal progression of non-target lesions, or appearance of new lesions.

Reminder:

- Response is judged against baseline, but progression is judged against the smallest recorded score.

Example:

Month	0	3	6	9	12
Measurement (mm)	100	90	50	55	≥ 60
Classification	Baseline	SD	PR	PR	PD

References:

Gehan EA and Tefft MC. Will there be resistance to the RECIST (Response Evaluation Criteria in Solid Tumours)? J Natl Cancer Inst 2000, 92, 179-181.

Appendix VI – Guidelines for the evaluation of resectability and histology

The consulting surgeon and the radiologist will determine resectability according to local practice. Spiral CT with injection of contrast medium, or MRI is mandatory. Patients with potentially resectable liver metastases can be included in the study.

Eligibility of patients with synchronous liver metastases and rectal cancer

1. Patients with synchronous liver metastases (LM) can undergo resection of the primary tumour first particularly if they have a risk of intestinal obstruction; these patients are eligible to be randomised in the protocol one month after the procedure. If resections of the primary tumour and LM are to be performed during the same procedure sufficient evidence that the primary tumour is completely resectable and that resection of primary cancer can be delayed for 3 to 4 months should be obtained (for example by CT scan or diagnostic laparoscopy) prior to randomisation. In patients with cancer of the rectum and synchronous liver metastases radiation therapy must not interfere with chemotherapy administered according to protocol.
2. If rectal and liver surgery are to be carried out at the same time no pre- or post-operative radiotherapy should be administered.
3. If surgical excision of rectal cancer is performed first, it must be decided before randomisation if radiotherapy will be administered or not. In any case, it should not delay treatment of liver metastases. Thus short pre-operative radiotherapy (Swedish scheme) is preferable.

Resectable liver metastases are defined as metastases which can be totally resected by surgery

1. With one or several anatomical resections provided the amount of remnant liver parenchyma after surgery is not less than 30% of total functional parenchyma.
2. With one or several wedge resections alone or in combination with anatomical resections.
3. The clearance between the tumour and the cut surface of the liver should be one centimeter or more whenever possible. However resection with a shorter clearance does not preclude inclusion in the study provided all tumour has been removed.
4. Patients with metachronous metastases must have undergone complete resection of the primary tumour without gross or microscopic evidence of residual disease (R0).

LM considered not resectable:

1. Tumours invading right and left branches of hepatic artery or portal vein.
2. Tumours extended to the 3 main hepatic veins.
3. Tumours that cannot be totally resected due to their size, location or number of deposit.
4. Association to liver metastases of extra hepatic cancer extension such as lung metastases. However the presence on chest CT scan of equivocal lesions measuring less than one centimeter is not considered a criteria for non inclusion. Note: tumour ablation techniques (cryosurgery, radiofrequency, laser hyperthermia) are not considered to be equivalent to resection.

When unexpected tumour extension is discovered at surgery, it should be managed by the most appropriate way and mentioned in CRF. In particular, if the number of metastases is higher than expected or if extrahepatic involvement is discovered it should be resected whenever possible.

Note: due to the risk of abdominal wall seeding, biopsy of the metastases prior to randomisation is not mandatory if the diagnosis is considered obvious according to the practice in each participating institution (i.e. if hepatic lesions are recent and have radiological characteristics of metastases, if tumour markers are elevated, etc.). In all cases metastases should be proven by biopsy during surgery even if unresectable.

When non-malignant disease cannot be ruled out, histology must be obtained prior to randomisation.

